### **Randomization**

For randomizing order of administration of niacin and placebo, investigators will assign consecutive code numbers to participants from prespecified lists stratified by group, sex, and BMI (95-99th percentile or >99th percentile). The NIH Clinical Center Investigational Drug Management and Research Section will use permuted blocks with stratification to generate the allocations that translate code numbers into study group assignments by using a pseudo-random number program. Pharmacy personnel not otherwise involved with the conduct of the study will dispense study capsules in containers that appear identical and differ only by participant code number. No participant, investigator, or other medical or nursing staff interacting with participants will be aware of study group assignments during the trial.

Arginine hydrochloride 10% solution is approved by the FDA for growth hormone testing. This agent is available through the NIH pharmacy and is on the formulary. It will be used at a dose of 500 mg/kg IV up to maximum of 30g infused over 30 min on two consecutive days. This dosing corresponds to 5 mL/kg, with a maximum dose of 300 mL on two consecutive days.

L-dopa is not approved by the FDA for growth hormone testing, but is approved for other uses. L-dopa has been used clinically for many years for the purpose of growth hormone testing. L-dopa powder will be obtained from Spectrum Chemicals, which has supplied us with a Certificate of GMP. From 2011-2016, L-dopa was packaged, supplied, and distributed to the inpatient staff by the NIH pharmaceutical development section as 250 mg capsules. The analytical group of

Pharmaceutical Development Service conducted testing according to USP standards for medications used in this protocol prior to release for human consumption. Starting in mid-2017, Pine Pharmaceuticals will compound the 250 mg capsules and perform bioburden testing per the United States Pharmacopeia (USP) <61> and <62> standards. Purity and stability testing will be performed by the NIH Investigational Drug Management and Research Section, which will track and dispense all medications to the inpatient staff.

### **Unblinding Procedure**

In this trial, all participants, Study Site staff, and pathology and laboratory personnel are blinded to the individual assignment of the order in which niacin and placebo are administered. Participants will learn their individual assignments (i.e., be unblinded) when the trial is complete. In rare instances, it may be necessary to unblind a participant's order of assignment before completion of the trial, to a physician, to the Study Site, or to the participant.

In general, however, participants should not be unblinded. Anytime a staff member learns the treatment assignment of a participant, the staff member is at risk of being influenced by that information. For example, if the unblinded participant was known to have taken the active agent and reported a toxicity, the staff member might make inferences about the effects of niacin on that participant, and possibly on other participants as well. The management of future participants may be influenced by this information. Maintaining the double-blind design offers the best protection against this potential bias.

In the unlikely event that a Serious and Unexpected Suspected Adverse Reaction (SUSAR) occurs and a physician must be unblinded to the treatment group to which an affected trial subject belongs, the Investigational Drug Management and Research Section (IDMS) will be contacted by a study investigator (usually by the Principal Investigator). The study investigator will request that IDMS release the needed information and specify the individual to receive the information. IDMS will normally supply unblinding information only to a physician who is not a co-investigator on the

study and make clear that group assignment must not be given to study investigators. This procedure is intended to ensure that the identity of the investigational medicinal product is revealed only insofar as is necessary. As much as possible, the blinding should be maintained for the investigators and for anyone responsible for data analysis or interpretation. A subject's treatment group should not be revealed to a study investigator except in a medical emergency, i.e. when this appears necessary to ensure the subject's safety and would be instrumental in further treatment decisions. If a subject's treatment is unblinded, this must be documented by IDMS in their written records. In all cases, the reasons and rationale for unblinding will be also documented in writing and maintained in the study file.

Unblinded data are also available to the Data Safety Monitoring Committee (DSMC). In the case of a SUSAR, the DSMC is informed and will thus have the opportunity to review subject-level data and make any changes to the experimental plan that are required. In the case of a SUSAR, the DSMC may elect to reveal the treatment group to which a subject belongs, request additional safeguards, or stop the study. The DSMC will assist investigators in deciding if a SUSAR requires any of the study investigators to become unblinded so that the FDA can be informed of subject assignment because of a SUSAR.

### **Study Administration and Data Collection, Management, and Storage**

The study will be conducted by the research team as listed above. Human biospecimens will be collected using procedures appropriate for the type of biospecimen being collected and will be handled in accordance with the U.S. Occupational Safety and Health Administration's Bloodborne Pathogens Standard for Samples. The principal investigator and the co-investigators will have access to identifiable participant records. Data will be coded by subject number, but will be readily associated with identifiable participant records. Records containing personal identifiers will be maintained consistent with the security measures required by the NIH. Data will either be transferred directly from the electronic medical record into the NICHD Clinical Trials Data Base (CTDB), or for data where direct transfer is unavailable, will be double-entered by hand into

CTDB. All data will be kept on secure computers in the SGO office, whose doors will be locked when staff is not present. All paper data will also be kept in locked areas in the SGO office. Serum and Plasma samples not analyzed immediately (as described above) will be stored in locked freezers by the NICHD sample management team supervised by the NICHD Clinical Director and tracked/managed through CTDB. Human biospecimens in storage will have a unique identifier, will be labeled with a printed label and will contain a barcode. Samples will be tracked using a computer-based inventory system that records the location and detailed information of every specimen in the repository.

Sample freezers will be operated using facility environments that include ambient temperature controls, good air circulation, lighting, and security. Systems are in place to allow for local and remote temperature monitoring of freezers. The NIH has an emergency preparedness plan that covers equipment failures and power interruption, including back-up storage capacity and back-up power generators.

Parents of participants give explicit permission regarding sample use in the consent form of the study, indicating if samples may be used for future experimental testing related to growth hormone response, body weight and metabolism without additional consent.

At the conclusion of the study, samples will be retained for future experimental testing related to growth hormone response, body weight and metabolism.

The PI will inform the IRB if samples are lost or destroyed before they are assayed for free fatty acids and growth hormone. Loss or destruction of samples saved only for future unspecified research will not be routinely reported, unless such loss also entails a breach of the Privacy Act.

### **Protection of Participants' Privacy and Confidentiality**

We will follow all relevant NIH policies and HRPP SOPs. Samples and data will be coded. Only individuals involved in consenting and patient care will have access to identifiers. Records

containing personal identifiers will be maintained consistent with the security measures required by the NIH. Access to the code will be limited to the study investigators. Electronic data will be password protected and accessible only by authorized study personnel. Electronic data will be backed up daily and stored at a secure server. All hardcopy data will be locked in [name] storage cabinets in research offices at the NIH Clinical Research Center and will be accessible only by authorized study personnel. All data will be collected specifically for the purpose of the current proposed research project. Any email communications that involve PII will be sent using encryption or the secure email system of the NIH. Since even when precautions are taken to ensure participant confidentiality, data collection in any study is accompanied by threat to privacy and confidentiality, in the unlikely event of a potential breach of confidentiality, the PI will immediately inform the IRB.

### **Limitations to the Study Design**

**We have identified several possible limitations to our study, including:**

- 1) Given that the GH stimulation tests are being performed on consecutive days, it is possible that effects of the first day's testing could carry-over to the second day and affect the results. However, many studies in the adult literature have used similar study designs. Furthermore, Cavallo et al showed no difference in response to GH stimulation testing on two consecutive days. Additionally, by randomizing the order of placebo or niacin given during the stimulation tests, we believe any effects of order will be detected.
- 2) Niacin is known to cause flushing shortly after administration. We anticipate that this side effect may conceivably lead the subjects and investigators to become aware of which day the niacin and placebo capsules were administered. We do not believe the blinding is critical to the success of the study given that we are only measuring objective hormonal data.

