**Table 2: Suppression of FFA <2 mEq/L by Niacin**

Group	Number of Subjects	Percentage of measurements post niacin with FFA <0.2 mEq/L
250 mg q 2H	2	11.5%
500 mg q 2H	5	43.1%
500 mg q 1H	5	67.5%

Adverse events during Dose Establishing Study 2 were largely as expected. All participants reported flushing or warmth, 60% tingling or rash, and 20-40% abdominal discomfort, nausea, or emesis.

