Stimulation testing will consist of arginine followed one hour later by L-dopa, both of which are standard medications used to assess GH secretion. Arginine is thought to inhibit somatostatin release, thereby allowing for GH secretion from the pituitary. Studies of the effect of arginine infusions on GHRH-stimulated GH release show enhanced GH response compared to GHRH alone. Furthermore, incubation of rat anterior pituitary cells with arginine shows no change in GH secretion, suggesting arginine is not itself a direct GH secretagogue but likely works by decreasing somatostatin tone. Arginine has been reported to produce long term changes in free fatty acid concentrations but no short term changes were seen after a single infusion. In contrast, L-dopa (L-3,4-dihydroxyphenylalanine) is thought to increase GHRH secretion, thereby promoting pituitary GH secretion. Studies of humans given GHRH antagonists showed suppressed GH concentrations after L-dopa administration, suggesting L-dopa's actions were blocked. In children with a robust GH response to L-dopa, GHRH plasma levels have also been found to rise in direct proportion to the GH response. Furthermore, studies combining L-dopa infusions with GHRH administration do not show enhancement of GH secretion compared to GHRH alone. Such results are not consistent with an effect of L-dopa on somatostatin release. We have chosen to use arginine and l-dopa in order to separately stimulate each hypothalamic hormone (GHRH and somatostatin) involved in growth hormone release and thus examine the physiologic effects of free fatty acids more carefully. We did not use GHRH as the stimulus because it would act directly on the pituitary and prevent us from examining the effects of niacin on the hypothalamus. We also chose not to use glucagon because it likely acts by two mechanisms, stimulating GHRH and inhibiting somatostatin via hypoglycemia.

We hypothesize that niacin will lead to a fall in free fatty acid concentrations in both groups and consequently a rise in stimulated GH secretion. We further hypothesize that the overweight subjects will demonstrate stimulated GH secretion profiles with niacin similar to those of control subjects who receive placebo.

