### **Data Analysis**

Primary research outcome will be niacin-induced changes in arginine and L-dopa stimulated GH concentrations, measured as both area under the curve and peak values, in the overweight group compared with the control group. Secondary research outcomes will include changes in free fatty acid, glucose, and insulin concentrations during the GH stimulation tests. Since non-completion of the study is expected to be due to technical failures (e.g., nonfunctioning IVs) rather than subject factors, all analyses will be limited to subjects who complete both placebo and niacin studies. We do expect that some members of the control group will not reach a peak GH concentration of 7 ng/mL during the stimulation testing. We will report all control subjects in the final analyses. Analyses will be performed with age, Tanner stage, and initial BMI-SDS as covariates. Furthermore, tertiary analyses will also be performed to compare subjects in the Tanner I, Tanner II, and Tanner III groups to determine if any differences exist among these pubertal development stages. This analysis will be for exploratory purposes only; the study is not powered for this subgroup analysis. Additionally if any members of the control group have abnormally elevated lipid levels, we will specifically examine these subjects and their growth hormone concentrations. The primary outcome analysis will therefore be a repeated measures ANCOVA with subject group (obese and control) as the between factor, treatment (niacin or placebo) as the repeated measure, GH concentration (peak and AUC) as the outcome variables, and age, sex, and Tanner pubertal stage as covariates. We will also model the subject group by treatment interaction but no other interaction terms will be entered into the primary analysis.

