### **Pharmaceutical information**

#### **Packaging and Labeling:**

Niacin will be purchased from Upsher-Smith Laboratories, Inc, as 500 mg tablets, USP, that have been manufactured according to GMP. Each table contains 500 mg of nicotinic acid. In addition, each tablet contains the following inactive ingredients: croscarmellose sodium, hydrogenated vegetable oil, magnesium stearate and microcrystalline cellulose. From 2011-2016, niacin, and the niacin placebo were packaged, supplied, and distributed to the inpatient staff by the NIH pharmaceutical development section. The study was placed on hold when use of all PDS-prepared compounds was quarantined in December 2016. Afterwards, starting in mid- 2017, all study compounds will be prepared following the same procedures by Pine Pharmaceuticals. The niacin study medication will be packaged as 250 mg capsules using a Swedish orange/caramel

opaque #1 capsule. The same capsule components used for the niacin will be used for the placebo.

From 2011-2016 PDS, and subsequently, Pine Pharmaceuticals, supplies inert placebo capsules that match the weight of the unlabeled niacin capsules. Pine Pharmaceuticals will perform bioburden testing per the United States Pharmacopeia (USP) <61> and <62> standards. Purity and stability testing will be performed by the NIH Investigational Drug Management and Research Section. Labels for medication will be computer generated by the NIH CRIS system.

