6. **Niacin:** We successfully applied for FDA approval for the use of niacin in children under an investigational new drug application (IND) with [name], PhD as sponsor. Niacin is currently FDA-approved in the United States, but only for adults. Niacin has been used off-label to treat hyperlipidemia in children. A retrospective chart review of 21 children, age 4 to 14, found one subject who developed a febrile illness with elevation in serum aminotransferase who was discontinued off niacin after two months. Reversible adverse effects of niacin included flushing (71%), itching (19%), abdominal pain (14%), nausea (14%), vomiting (14%), headache (14%), and constipation (5%). 29% also demonstrated reversible dose-related elevations in AST concentrations. Niacin is known to cause transient skin flushing likely due to prostacyclin formation leading to cutaneous blood flow. In some trials testing GH secretion in adults, flushing has been observed after niacin

with rapid resolution. In the event of intolerable flushing as reported subjectively by the patient, we will administer a single dose of 10 mg/kg of ibuprofen to help alleviate the reaction. Nausea, vomiting, and temporary tightness of the chest have also been noted in some subjects. No other side effects have been noted in these studies; however, in uses of niacin to treat hyperlipidemia, the following other side effects have infrequently been reported: atrial arrhythmias, dental pain, liver injury, myalgia, myopathy, skin rashes, peptic ulcers, gastrointestinal bleeding as well as bleeding from other sites, diarrhea, onset of diabetes and worsening of diabetic control, infections, blurred vision and macular degeneration. Additionally the effects of niacin in pregnancy are unknown.

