## Appendix A

Medications Used in Growth Hormone Stimulation Testing						
Test	Dose	Timing of peak GH	Mechanism	Side effects	Cutoff GH value for <math>\geq 90\%</math> sensitivity	Cutoff GH value for <math>\geq 90\%</math> specificity
Arginine	0.5 g/kg IV to max of 40 g, infuse over 30 min	30-60 min	Inhibits somatostatin	Late hypoglycemia		
L-Dopa	125 mg for < 13.5 kg 250 mg for 13.5-31.5 kg 500 mg for > 31.5 kg	20-120 min	$\alpha$ -adrenergic stimulation of GHRH	Nausea, emesis, headache	26.6	11.1
GHRH	1 or 2 mg/kg, infuse over 1 min	15-30 min	Stimulates pituitary somatotrophs	Flushing		
Glucagon	0.03 mg/kg to max of 1 mg, give IM or SC	2-3 h	Increases insulin	Late hypoglycemia	29.4	7.5
Insulin	0.05-0.1 units/kg, give as bolus	30-60 min	Stress response to hypoglycemia presumed to decrease somatostatin	Severe hypoglycemia	23.4	2.2
Clonidine	5 mcg/kg to max of 250 mcg	60 min	$\alpha$ -2 agonist stimulates GHRH and inhibits somatostatin	Drowsiness, hypotension	30.5	8.2

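### GH and FFA are analysed separately, so the plan can show that niacin raises GH but cannot say whether the fall in FFA is the reason

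*Combined protocol and SAP*

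**What the plan says.** **The causal claim.** The overview of the pilot study predicts "a fall in free fatty acid concentrations in both groups and consequently a rise in stimulated GH secretion". Objectives sets out to determine the effect of inhibiting lipolysis, not only of giving niacin. The third of the Specific Hypotheses expects peak GH in obese children to rise on niacin to about the level of non-GH-deficient controls on placebo.

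**The analysis.** Data Analysis specifies a repeated measures ANCOVA of GH (peak and AUC) with group, treatment, their interaction, age, sex and Tanner stage. On FFA it says only: "Secondary research outcomes will include changes in free fatty acid, glucose, and insulin concentrations during the GH stimulation tests". It lists no term or analysis for FFA as a predictor of GH, for symptoms, or for ibuprofen.

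**The comparator.** Packaging and Labeling describes "inert placebo capsules that match the weight of the unlabeled niacin capsules". For the regimen carried into the main study, the report of Dose-Establishing Study 2 states: "All participants reported flushing or warmth, 60% tingling or rash, and 20-40% abdominal discomfort, nausea, or emesis". Under Risks and Discomforts, item 6: "In the event of intolerable flushing as reported subjectively by the patient, we will administer a single dose of 10 mg/kg of ibuprofen".

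**The blind.** Limitations to the Study Design accepts that flushing may reveal the niacin day, then says: "We do not believe the blinding is critical to the success of the study given that we are only measuring objective hormonal data".

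**Symptom capture.** Under Adverse event reporting and Appendix D, the main-study questionnaire is completed once, at the end of a stay that covers both test days. It has no field for the day.

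**The concern.** The reply about objective data addresses one threat only: that someone who knows the treatment day might record the outcome differently. A second threat is that the child's body responds to the reaction (flushing, nausea, discomfort), or to a drug given to relieve it, and that this response alters GH. A perfect assay would measure that response faithfully.

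The documents make such a route conceivable without showing that it operates. Appendix A gives the insulin test's mechanism as "Stress response to hypoglycemia presumed to decrease somatostatin", so a non-FFA route to GH release is acknowledged, although only for hypoglycemia.

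What is at stake is the interpretation. The overview says it is not known whether children respond to raised FFA, to other factors, or to both. Separating these is part of the study's purpose, and as planned a GH rise and an FFA fall would be reported side by side with nothing testing whether they go together in the same child.

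**Working it through.** **1. The plan's own figures.** Determination of Sample Size uses a difference of 10 µg/L, SD 6.1 and alpha 0.05. It states 14 per group (80% power) and 22 per group (95%). A two-sided two-sample t-test gives 7 and 11 per group (power 0.804 and 0.955), that is, 14 and 22 in total. With SD 6.1 × √2 = 8.63 it gives 13 and 21 per group. Allowing for 20% dropout, 40 / 0.8 = 50, as stated. Whether 14 and 22 are totals is a separate matter; the target of 20 completers per group is taken as given here.

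**2. How far the reactions differ between days.** Data Table 3 has n = 5, so 20% is one child, and time 0 precedes the first dose. The peak minus time 0 is:

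- Flushing: 100% − 0% = five children
- Feeling warm: 100% − 40% = three children
- Nausea: 40% − 20% = one child
- Stomach ache: 40% − 20% = one child
- Vomiting: 20% − 0% = one child (at hours 1 and 4; none at hours 2 and 3)

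The imbalance is plain for flushing and warmth and slight for gastrointestinal symptoms. Items 7 and 8 of the risk section also list nausea and vomiting for L-dopa and arginine, and flushing for arginine. Both drugs are given on both days.

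**3. Which comparisons carry a reaction effect.** For group g (o = obese, c = control), let B be mean GH on placebo, L the effect of niacin through FFA, and R its effect through the reaction.

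- Niacin minus placebo within a group: L_g + R_g
- Group-by-treatment interaction: (L_o − L_c) + (R_o − R_c), which is free of R if R_o = R_c
- Within-obese rise: L_o + R_o
- Obese on niacin minus control on placebo: B_o + L_o + R_o − B_c

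The last two, which the third hypothesis uses, keep R_o. In every line the total effect of niacin is estimated validly. Only the split between L and R is unknown.

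**4. How small a non-FFA rise would be significant.** Assume that 6.1 is the SD of the within-child change; the plan does not say so clearly. With 20 obese completers, the smallest significant mean is t(0.975, 19) × 6.1 / √20 = 2.093 × 1.364 = 2.85 µg/L. That is 2.85 / 10.3 = 28% of the increase taken from the adult acipimox data. Significance alone therefore does not identify the mechanism. This is a threshold, not an estimate of R.

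**5. What a GH-on-FFA analysis could detect.** By Fisher's z, the smallest |r| with 80% power is tanh[(1.960 + 0.842) / √(n − 3)].

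- n = 40: tanh(2.802 / 6.083) = 0.43
- n = 20 (one group): tanh(2.802 / 4.123) = 0.59

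The data will exist: the Outline of Main Study Blood Draws shows GH and FFA sampled together at every time point.

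**The case against.** Several points on the other side stand.

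- **The group comparison is largely protected.** The primary outcome compares niacin-induced change between groups, and a similar reaction effect in both groups cancels.
- **The stress route is an extrapolation.** Appendix A's entry concerns hypoglycemia. Nothing in the documents says that flushing, nausea or ibuprofen raises GH. In Dose-Establishing Study 1 at 500 mg, flushing reached 80% and warmth 100%, yet GH rose only slightly and not significantly. Five children without placebo settle nothing, but this does not point to a large reaction effect.
- **No analysis of these data can fully separate the routes.** Niacin exposure drives both the FFA fall and the reactions, so a correlation would not prove mediation. The regimen was chosen for consistent suppression (67.5% of post-dose measurements below 0.2 mEq/L), which may narrow the spread of FFA change and weaken any correlation. A null result would not refute the mechanism.

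GHRH and somatostatin are also sampled, and the two stimuli were chosen to probe each pathway. This helps less than it seems. Data Analysis does not list either hormone, and a fall in somatostatin could accompany a stress response as well as an FFA effect.

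A reader might also infer that vomiting on the niacin day would lose oral L-dopa and lower GH. The timing gives this little support. L-dopa at 9:30am corresponds to hour 2 of Data Table 3, and vomiting was reported only at hour 1, before it, and at hour 4, the time of the last sample.

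**Conclusion.** The point holds as one of attribution. The plan states a mechanism, collects the data that bear on it, and specifies no analysis connecting them. Its defence of the weak blind does not cover a physiological response to the reaction. The affected claims are that lipolysis explains the within-obese rise and the obese-on-niacin versus control-on-placebo comparison.

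Three stronger readings are not supported:

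- **That the estimated effect of niacin on GH is invalid.** It is a valid effect of niacin, by whatever route.
- **That the bias can be sized.** Supposing that 20–40% of children react and gain 5–10 µg/L would shift the mean by 0.20 × 5 = 1 to 0.40 × 10 = 4 µg/L. The 5–10 has no basis in the documents, and the 20–40% ignores symptoms present before dosing and on placebo days. The direction is also uncertain.
- **That the plan commits to concluding for lipolysis.** Data Analysis contains no such decision rule, and the rationale for subject selection speaks of the effect of niacin.

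The 2.85 µg/L threshold rests on reading 6.1 as a within-child SD and on 20 obese completers.

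**What to change.** 1. **Data Analysis.** Pre-specify a supportive secondary analysis: regress each child's niacin-minus-placebo GH change (peak and AUC) on the same child's niacin-minus-placebo FFA change over the same window, with group in the model. Report the slope with its confidence interval. Present it as a test of a necessary prediction of the FFA mechanism, not as proof of mediation and not as a pass/fail criterion.
2. **Conclusions.** Word the main conclusion as an effect of niacin on GH, and state whether this analysis supports attribution to FFA.
3. **Limitations to the Study Design.** Amend the sentence on blinding to say that objective assays remove observer bias but do not exclude a physiological response to the reaction.
4. **Recording.** Record symptoms and any ibuprofen by day and clock time. Any sensitivity analysis on vomiting or ibuprofen depends on this and should be labelled exploratory.

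Cost: wording changes and a small addition to recording, with no new samples. The drawback is modest power: with 40 children only a fairly strong association is likely to be detected, so the confidence interval matters more than the p-value.
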